5.3 Endpoints

5.3.1 Primary Endpoints

The following PK parameters will be analyzed for TAK-788.

- Time of first occurrence of C_{max} (T_{max}).
- Maximum observed concentration (C_{max}).

- Area under the concentration-time curve from time 0 to infinity, calculated using the observed value of the last quantifiable concentration (AUC_∞).
- Area under the concentration-time curve from time 0 to the time of the last quantifiable concentration (AUC_{last}).

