9.3.1 PK Measurements

9.3.1.1 Plasma PK Measurements

PK parameters from plasma concentrations of TAK-788 and its metabolites, AP32960 and AP32914, will be calculated as follows, as appropriate, following oral administration:

AUC _{last} :	The area under the concentration versus time curve, from time 0 to the last observed non-zero concentration, as calculated by the linear trapezoidal method.
AUC _∞ :	The area under the concentration versus time curve, from time 0 extrapolated to infinity. AUC _∞ is calculated as AUC _{last} plus the ratio of the last measurable blood concentration to the elimination rate constant.
AUC _{%extrap} :	Percent of AUC _∞ extrapolated, represented as (1 – AUC _{last} /AUC _∞)*100.
CL/F:	Apparent total plasma clearance after oral (extravascular) administration, calculated as Dose/AUC _∞ (TAK-788 only).
C _{max} :	Maximum observed concentration.
t _{max} :	Time to reach C _{max} . If the maximum value occurs at more than one time point, t _{max} is defined as the first time point with this value.
t _{½z} :	Apparent first-order terminal disposition phase half-life will be calculated as 0.693/λ _z .
λ _z :	Apparent first order terminal disposition phase rate constant calculated from a semilog plot of the plasma concentration versus time curve.
Vz/F:	Apparent volume of distribution during the terminal disposition phase after oral (extravascular) administration, calculated as Dose/(AUC _∞ × λ _z) (TAK-788 only).

No value for λ_z, AUC_∞, AUC_{%extrap}, CL/F, Vz/F, or t_{½z} will be reported for cases that do not exhibit a linear terminal log-linear phase in the concentration versus time profile.

No PK parameters will be calculated for subjects with detectable concentrations at 2 or fewer consecutive time points.

Individual and mean plasma concentration-curves (both linear and log-linear) will be included in the final report.

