11.1.3.1 Analysis of Variance

A linear mixed-effects model will be used for the analysis on the ln-transformed C_{max} , AUC_{∞} , and AUC_{last} for TAK-788 and its active metabolites (AP32960 and AP32914). The model will include sequence, treatment, and period as a fixed-effect and subject nested within sequence as a random-effect. Each model will include calculation of LSMs as well as the difference between treatment LSMs.

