11.1.3.2 Ratios and Confidence Intervals

GMR and 90% CI, consistent with the two one sided test [Schuirmann 1987], will be calculated using the exponentiation of the difference between treatment LSMs from the analyses on the ln-transformed C_{max} , AUC_{∞} , and AUC_{last} (if it is needed) for TAK-788 and the combined molar C_{max} , AUC_{∞} , and AUC_{last} (if it is needed) for TAK-788 and its active metabolites. These ratios will be expressed as a ratio of test treatment relative to the appropriate reference treatment.

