### **4.4 Study Design**

This is an open-label, randomized, 2-period, and 2-sequence crossover high-fat meal effect study in healthy adult subjects.

Subjects will undergo screening evaluations to determine eligibility within 21 days prior to dosing. Subjects will be admitted to the clinical facility the day prior to dosing in each period (Day -1). Subjects will be randomized on Day 1 of Period 1 to a crossover sequence in a 1:1 ratio and administered a single oral dose of 160 mg of mobocertinib with or without a high-fat meal on Day 1 of each period (i.e., Period 1 and Period 2). Each dose will be separated by a washout period of 10 days. Blood samples for mobocertinib PK will be collected predose and up to 240 hours following each mobocertinib dose.

Subjects will receive the following treatments on one occasion in a crossover fashion to evaluate the effect of a high-fat meal:

- Treatment A: Administration of a single oral dose of 160 mg mobocertinib (4 x 40 mg capsules) following an overnight fast.
- Treatment B: Administration of a single oral dose of 160 mg mobocertinib (4 x 40 mg capsules) with a high-fat meal.

\* 800-1000 total calories, 500-600 calories, 55-65 g, or 50% from fat

Subjects will remain at the clinical site until the 240-hour study assessments in Period 2 are completed. All doses of mobocertinib will be administered at the clinic during this study. A final safety follow-up phone call will occur  $30 \pm 2$  days after the last mobocertinib dose to determine if any adverse events (AEs) have occurred since the last study visit. Replacement of discontinued or withdrawn subjects due to any reason will be assessed on a case by case basis by the Sponsor and the Principal Investigator (PI) to ensure a minimum of 12 PK-evaluable subjects complete the study.

Any subject who experiences emesis within 8 hours postdose will be excluded in the final PK data analysis and may be replaced with a new subject.

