## **6.0 DETERMINATION OF SAMPLE SIZE**

The sample size calculation was based on the expected 2-sided 90% confidence interval (CI) for the difference in the paired, log-transformed  $AUC_{\infty}$  means of mobocertinib in the presence and absence of a high-fat meal. The within-patient coefficient of variation for mobocertinib  $C_{\max}$  was estimated to be 17.2% on the basis of data from a clinical study conducted in healthy subjects (TAK-788-1001). If the observed geometric mean ratio (GMR) for the mobocertinib  $AUC_{\infty}$  in the presence and absence of high-fat is 1, with a sample size of 12, the 90% CI for the  $AUC_{\infty}$  GMR is expected to be 0.881 to 1.13 on the basis of the variance assumptions. Fourteen (14) adult subjects will be enrolled into this high-fat meal effect study to get at least 12 PK-evaluable subjects in each treatment according to the Food and Drug Administration (FDA) guidance Assessing the Effects of Food on Drugs in Investigational New Drugs (INDs) and New Drug Applications (NDAs) – Clinical Pharmacology Considerations Guidance for Industry (FDA food effect [FE] 2019).

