### **Food Effect**

For evaluation of potential effect of a high-fat meal on mobocertinib PK, a linear mixed-effects model will be used for the analysis on the ln-transformed  $C_{max}$ ,  $AUC_{\infty}$ , and  $AUC_{last}$  (only if  $AUC_{\infty}$  is not available for at least 12 subjects) for mobocertinib (mass units) and combined molar  $C_{max}$ ,  $AUC_{\infty}$ , and  $AUC_{last}$  (only if  $AUC_{\infty}$  is not available for at least 12 subjects) for mobocertinib, AP3260, and AP32914. The mixed effects models will include sequence, treatment, and period as fixed effects, and subject nested within sequence as a random effect. Each model will include calculation of LSMS as well as the difference between LSMS.

GMR and 90% CIs, consistent with the two one-sided tests, will be calculated using the exponentiation of the difference between treatment LSMS from the analyses on the ln-transformed  $C_{max}$ ,  $AUC_{\infty}$ , and  $AUC_{last}$  (only if  $AUC_{\infty}$  is not available for at least 12 subjects) for mobocertinib, as well as the ln-transformed molar combined  $C_{max}$ ,  $AUC_{\infty}$ , and  $AUC_{last}$  (only if  $AUC_{\infty}$  is not available for at least 12 subjects) for mobocertinib, AP32960, and AP32914. The comparison of interest is as follows:

Treatment B (High-Fat Meal) relative to Treatment A (Fasted)

The following SAS code will be used:

```
PROC MIXED DATA=XXXX;  
CLASS Treatment Subject Period Sequence;  
MODEL <PK_Parameter> = Treatment Period Sequence / DDFM=KR;  
RANDOM Subject(Sequence);  
ESTIMATE 'Treatment B vs A' Treatment -1 1 / CL ALPHA = 0.10 E;  
LSMEANS Treatment;  
Run;
```

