### **7.15 Changes in the Statistical Analysis Plan**

Section 11.1.3.1 of the protocol stated that  $AUC_{last}$  will be included in the ANOVA for TAK-788. However, Section 11.1.3.2 of the protocol stated that  $AUC_{last}$  will be included in the calculation of GMR and 90% CI only if it is needed. The SAP clarified that  $AUC_{last}$  will be included in the ANOVA only if  $AUC_{\infty}$  is not available for at least 12 subjects.

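### SAP 7.10.1 withholds the fed-versus-fasted estimate for mobocertinib AUClast, an unconditional primary endpoint, unless AUC∞ runs short; removing the condition costs one model run

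*SAP*

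**What the plan says.** Protocol 5.3.1 lists four primary parameters for TAK-788 (mobocertinib in the SAP): tmax, Cmax, AUC∞ and AUClast. The AUClast entry, "Area under the concentration-time curve from time 0 to the time of the last quantifiable concentration", carries no condition, and SAP 5.1 repeats the list.

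The protocol's analysis sections differ from each other. Section 11.1.3.1 states "A linear mixed-effects model will be used for the analysis on the ln-transformed" Cmax, AUC∞ and AUClast, again without condition. Section 11.1.3.2 and the synopsis give the GMR and 90% CI for AUClast with the rider "if it is needed) for TAK-788 and the combined molar" parameters, and do not define when it is needed.

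SAP 7.15 reports that difference and settles it: AUClast "will be included in the ANOVA only if" AUC∞ falls short for 12 subjects. SAP 7.10.1 writes the condition in four places: in the model sentence and in the GMR/CI sentence, each time for mobocertinib and for combined molar exposure. The first instance reads, of AUC∞, "is not available for at least 12 subjects) for mobocertinib (mass units) and combined molar" parameters. Whether or not the condition is met, SAP 7.10.1 has the PK parameters listed and summarised by treatment.

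AUC∞ can be missing where AUClast is not. Under protocol 9.3.1.1 no AUC∞ value "will be reported for cases that do not exhibit a linear terminal log-linear phase in the concentration versus time profile".

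**The concern.** The primary objective is to characterise a food effect in a crossover, so the informative summary of an exposure parameter is the within-subject ratio with its interval. Under the SAP rule one of the listed primary exposure measures would normally get no such ratio, only summaries by treatment.

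The omission matters most when a few AUC∞ values are missing. AUClast needs no terminal slope, so it survives for profiles that lose AUC∞. A paired AUClast estimate on all evaluable subjects is then the natural check on whether the AUC∞ ratio depends on which subjects remain. The rule withholds that check while at least 12 subjects still have AUC∞.

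**Working it through.** **1. The documents side by side, for mobocertinib AUClast.**

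| Place | Status of AUClast |
|---|---|
| Protocol 5.3.1, SAP 5.1 | Primary endpoint, no condition |
| Protocol 11.1.3.1 | Modelled, no condition |
| Protocol 11.1.3.2, synopsis | GMR and CI only if needed; not defined |
| SAP 7.10.1, 7.15 | Model, GMR and CI only if AUC∞ falls short for 12 subjects |

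Combined molar AUClast is different. It is not in the primary endpoint lists or in protocol 11.1.3.1, and protocol 11.1.3.2 already makes it conditional.

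**2. The plan's own figure.** Inputs from SAP 6.0: within-subject CV 17.2% (stated for Cmax), n = 12, observed GMR 1, two-sided 90% CI.
- s_w = √ln(1 + 0.172²) = 0.1707
- Log half-width = t(0.95; 10 df) × s_w × √(2/12) = 1.812 × 0.1707 × 0.4082 = 0.126
- CI = exp(±0.126) = 0.881 to 1.135, which agrees with the plan's 0.881 to 1.13.

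**3. How often would the gap arise?** The gap is the case where at least one subject lacks an AUC∞ pair but 12 or more still have one, so AUClast is not modelled. The documents give no AUC∞ loss rate. I assume a loss q of 1% to 10% per profile, independent between profiles, and read the trigger as fewer than 12 subjects with AUC∞ under both treatments. A subject keeps the pair with probability p = (1 − q)². With N evaluable subjects and X ~ Bin(N, p), the gap is P(12 ≤ X ≤ N − 1).

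Example, N = 14 and q = 5%: p = 0.9025, and P(X = 12) + P(X = 13) = 0.253 + 0.360 = 0.612.

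| q | p | Gap, N = 14 | Gap, N = 13 | Gap, N = 12 |
|---|---|---|---|---|
| 1% | 0.9801 | 24% | 20% | 0 |
| 2% | 0.9604 | 42% | 32% | 0 |
| 5% | 0.9025 | 61% | 37% | 0 |
| 10% | 0.8100 | 43% | 20% | 0 |

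With N = 12 any lost pair fires the trigger, so AUClast is modelled; at q = 1% that has probability 1 − 0.9801¹² = 21%. Clustering of losses within subjects would lower the chance that any pair is lost.

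**4. How far could the AUC∞ estimate move?** The SD of a within-subject log ratio is √2 × 0.1707 = 0.2415. For random loss and a complete-pair analysis, the SD of the shift in the log GMR is:
- one of 14 lost: 0.2415 × √(1/13 − 1/14) = 0.018
- two of 14 lost: 0.2415 × √(1/12 − 1/14) = 0.026, or 0.026/0.126 ≈ 0.21 of the planned half-width.

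Loss related to the food effect would not follow this formula, and the paired AUClast estimate is the check for that case.

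**5. The count of 12.** SAP 4.4 speaks of replacement "to ensure a minimum of 12 PK-evaluable subjects complete the study"; SAP 6.0 speaks of enrolling 14 "to get at least 12 PK-evaluable subjects in each treatment according to the" guidance it cites. Neither is tied to the AUC∞ trigger. The two counts can differ: with 14 subjects and 12 AUC∞ values under each treatment, complete pairs number between 2 × 12 − 14 = 10 and 12. The question disappears for mobocertinib if the condition is removed.

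**The case against.** The strongest reply is that this was decided openly. The protocol's two sections disagree, SAP 7.15 says so, and the SAP gives content to an undefined phrase in 11.1.3.2. Protocol 11.1 allows the SAP to modify planned analyses and asks for an amendment only for major changes to the primary analysis. That stands. A reader might infer a concealed departure from the protocol or a missing amendment; the documents do not support this, because the change is disclosed and one protocol section already made the AUClast interval conditional.

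It can also be said that a primary endpoint here need not have a model. Protocol 5.1 states that a hypothesis is not applicable, the objective is descriptive, the sample size rests on AUC∞, and AUClast is still summarised. This limits the importance of the point, but the documents give no reason for withholding an inexpensive paired estimate.

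A reader might extend the complaint to combined molar AUClast. The documents do not support that, as step 1 of the working shows.

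A reader might also make the undefined count the main fault. It is missing detail. Complete pairs is a reasonable reading, and the CPAP, not available here, covers insufficient terminal-phase data and may add to it.

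Finally, the documents report no difficulty in estimating AUC∞. Sampling runs to 240 hours, and AUC∞ results are quoted from two earlier studies in healthy subjects. Losses may be rare.

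**Conclusion.** The point holds as a minor, nearly free improvement. Mobocertinib AUClast is listed as primary and modelled in protocol 11.1.3.1 without condition, yet under SAP 7.10.1 it gets no within-subject food-effect estimate unless AUC∞ is short. This is a disclosed choice with a small cost to interpretation, not an error. Cmax and AUC∞ inference is unaffected.

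The gap probabilities rest on assumed, independent loss rates and a complete-pair count. They also depend strongly on how many of the 14 are evaluable. Quoting the 24% to 61% range alone would suggest that the gap is likely; the documents support no such statement, and with 12 evaluable subjects it cannot occur. Nor do they show that the AUC∞ result would be biased. They show only that the simplest check would not be reported.

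**What to change.** In SAP 7.10.1 (Food Effect), delete the condition on mobocertinib AUClast in both the model sentence and the GMR/CI sentence. Report its GMR and 90% CI in all cases, next to Cmax and AUC∞. Revise SAP 7.15 to say that mobocertinib AUClast is modelled without condition, as in protocol 11.1.3.1.

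Treating combined molar AUClast in the same way is an optional extension for consistency. If its condition is kept, state that the 12 are subjects with combined molar AUC∞ under both treatments. The rider in protocol 11.1.3.2 and the synopsis can be aligned at the next amendment; none is needed for this alone.

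The cost is one further run of the PROC MIXED code already in the SAP, or two with combined molar, plus the wording changes. No new data are needed.

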#### **Nonparametric Analysis of $t_{max}$**

A nonparametric analysis for  $t_{max}$  will be performed to compare treatment differences using the Wilcoxon Signed Rank test. Median difference (Test-Reference), the Hodges-Lehmann estimator, and estimated confidence interval will be used to examine the location shift in  $t_{max}$ . The  $t_{max}$  parameter will not be ln-transformed. The median difference, associated 95% CI, and p-value will be presented.

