7.7 Subject Replacement

Replacement of discontinued or withdrawn subject(s) due to any reason will be assessed on a case by case basis by the Sponsor and PI to ensure a minimum of 12 PK-evaluable subjects complete the study.

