9.1.1.1 Assignment of Screening and Allocation Numbers

Each subject will be assigned a unique identification number upon screening. Subjects who complete the study screening assessments and meet all the eligibility criteria will be assigned a unique identification number at the time of the first dosing, different from the screening number.

If replacement subjects are used, the replacement subject number will be 100 more than the original (eg, Subject No. 101 will replace Subject No. 1).

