**Table 7:1 Collection of Blood Samples for Pharmacokinetic Analysis**

Analyte	Matrix	Sampling Day	Period	Scheduled Time (hours)
mobocertinib, AP32960, and AP32914	Plasma	1	1 and 2	Predose and 0.5, 1, 2, 4, 6, 8, 12, 24, 48, 72, 120, 168, and 240 hours postdose (a) (b)

(a) If a subject experiences a serious adverse event (SAE), a blood sample for PK analysis should also be obtained at the unscheduled visit. PK samples will be collected at Early Termination at the discretion of the PI.

(b) The Period 1 Day 11 PK sample will serve as the pre-dose PK sample for Period 2.

The actual date and time of sample collection will be recorded on the source document in the CRF.

Concentrations will be listed and summarized descriptively by PK sampling time in mass units for plasma mobocertinib, AP32960, and AP32914. Summary will be done by treatment using the summary statistics listed in the CPAP. Excluded concentrations will be presented and footnoted as such in the concentration table listings, and those values will be excluded from the descriptive summary statistics. Individual subject and arithmetic mean profiles of the concentration-time data will be plotted by treatment on linear (with and without SD) and semi-log scales in mass units for each analyte. For summary statistics and arithmetic mean plots by sampling time, the nominal PK sampling time will be used, for individual subject plots by time, the actual PK sampling time will be used.

The PK parameters of mobocertinib, AP32960, and AP32914 listed in the CPAP for this study will be determined from the concentration-time profiles for subjects in the PK set using a noncompartmental analysis method in mass units. The molar  $AUC_{last}$ ,  $AUC_{\infty}$ , and  $C_{max}$  PK parameters will also be calculated for plasma mobocertinib, AP32960, and AP32914 using the molecular weights of each analyte as outlined in the CPAP. Combined molar  $AUC_{last}$ ,  $AUC_{\infty}$ , and  $C_{max}$  for plasma mobocertinib, AP32960, and AP32914 will also be presented. Actual sampling times, rather than scheduled sampling times, will be used in all computations involving sampling times. If actual sample times are missing, nominal times may be used.

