### **7.14 Preliminary Analysis**

Analysis will be completed as described in the CPAP and Section [7.10.1](#) of the SAP, with the following changes: 1) QCed data will be used (not QAed); 2) nominal times will be used for the calculation of PK parameters (not actual sampling times); 3) tables and figures will be created using Phoenix® WinNonlin® Version 8.1 or higher.

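### Should the tmax analysis adjust for period, as the Cmax and AUC models do?

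*SAP*

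**What the plan says.** SAP 5.1 and Protocol 5.3.1 list tmax as a primary endpoint beside Cmax, AUC∞ and AUClast. For tmax, SAP 7.10.1 states that a nonparametric analysis "will be performed to compare treatment differences using the Wilcoxon Signed Rank test", with a Hodges-Lehmann estimate of the location shift, untransformed, and adds: "The median difference, associated 95% CI, and p-value will be presented". No period or sequence term is mentioned.

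Under Food Effect, the same section says of ln Cmax and ln AUC: "The mixed effects models will include sequence, treatment, and period as fixed effects". The SAS code there agrees. Protocol 11.1.3 names no test for tmax, and SAP 7.15 does not mention tmax.

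The sampling schedule is "Predose and 0.5, 1, 2, 4, 6, 8, 12, 24, 48, 72, 120, 168, and 240 hours postdose", and "Actual sampling times, rather than scheduled sampling times, will be used in all computations involving sampling times". Nominal times serve only the preliminary analysis (SAP 7.14).

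Fourteen subjects are randomised 1:1 to AB and BA. Protocol 7.7 decides replacement case by case "to ensure a minimum of 12 PK-evaluable subjects complete the study". Protocol 9.1.1.1 adds that "the replacement subject number will be 100 more than the original", which ties each replacement to a particular subject but does not say in words that the sequence carries over.

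**The concern.** One SAP section removes period from some primary endpoints and leaves it in another, without giving a reason. The washout rationale in Protocol 6.2.1 deals with carryover, which is a different matter.

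If tmax drifts between periods, pooling mixes two groups of differences with different centres. At equal sequences this adds spread, so the interval widens and the test becomes conservative. At unequal sequences the shift itself moves, in a direction set by which sequence lost subjects. Unequal sequences can occur within the plan: 13 evaluable subjects are always unbalanced, and two unreplaced random losses from 7:7 leave 7:5 or 5:7 with probability 2 × C(7,2)/C(14,2) = 42/91 = 46%. At stake would be the accuracy of a reported primary-endpoint shift and its interval.

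**Working it through.** **The plan's own figure.** The documents give no precision figure for tmax. The only one is the 90% CI of 0.881 to 1.13 for the AUC∞ ratio (Protocol 11.2, SAP 6.0). With s = √ln(1 + 0.172²) = 0.171, n = 12 and 10 degrees of freedom, exp(±1.812 × 0.171 × √(2/12)) gives 0.881 to 1.135. It reproduces, but it does not bear on tmax.

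**Mechanism.** Let δ be the food effect and π the Period 2 minus Period 1 effect. B − A centres on δ + π in AB and on δ − π in BA. The pooled mean is therefore δ + π(nAB − nBA)/n. The bias is 0 at 7:7 and 6:6, π/13 at 7:6 and π/6 at 7:5.

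**Simulation inputs.** Fasted median 4 h is the patient median in Protocol 4.1. Within-subject log-SD 0.3, between-subject log-SD 0.2 and a 1.5-fold food effect are assumptions, each at a single value. Peaks were set to the nearest scheduled time, and actual times were spread over 30% of the Protocol Table 3.a windows unless stated. Settings used 20,000 trials each. The alternative is a rank-sum test and two-sample Hodges-Lehmann shift on half period differences, AB against BA. On the log scale the SD of a within-subject difference is 0.3 × √2 = 0.42, so period effects of 1.1-, 1.25- and 1.5-fold are about 0.2, 0.5 and 1.0 SD.

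**Bias (no food effect).** At the median, 1.25-fold is 1 h and 1.5-fold is 2 h.

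| Split | Period effect | By formula | Simulated, planned |
|---|---|---|---|
| 7:6 | 1.25-fold | 1/13 = 0.08 h | 0.07 to 0.08 h |
| 7:5 | 1.25-fold | 1/6 = 0.17 h | 0.16 to 0.17 h |
| 7:5 | 1.5-fold | 2/6 = 0.33 h | 0.35 to 0.37 h |

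The adjusted shift is within about 0.01 h of zero at these splits.

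**Variability of the estimate (no food effect), SD, planned v adjusted.**

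| Split | No period effect | 1.25-fold | 1.5-fold |
|---|---|---|---|
| 7:7 | 0.56 v 0.60 h | 0.61 v 0.65 h | 0.67 v 0.70 h |
| 6:6 | 0.61 v 0.64 h | 0.66 v 0.68 h | 0.72 v 0.75 h |

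Root mean squared error, which counts the bias: 7:5 at 1.25-fold, 0.69 v 0.71 h; 7:6 at 1.5-fold, 0.72 v 0.72 h; 7:5 at 1.5-fold, 0.81 v 0.77 h. Only the last clearly favours adjustment.

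**Power with the food effect, and mean 95% CI width, planned v adjusted.**

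| Period effect | Power 7:7 | Power 6:6 | Power 7:5 | CI width 6:6 |
|---|---|---|---|---|
| None | 80.8 v 78.1% | 72.8 v 69.6% | 72.5 v 68.5% | 3.20 v 3.38 h |
| 1.1-fold | – | 72.3 v 70.7% | – | 3.40 v 3.53 h |
| 1.25-fold | 74.9 v 78.7% | 65.1 v 70.4% | 72.9 v 68.8%* | 3.94 v 3.80 h |
| 1.5-fold | – | – | – | 5.25 v 4.28 h |

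*The planned test is helped here by its bias; at 5:7 the figures are 55.9 v 69.3%.

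**Type I error.** At 6:6 the planned test rejects a true null in 4.5, 4.3, 3.1 and 0.9% of trials as the period effect rises through 1.0, 1.1, 1.25 and 1.5-fold. At splits from 7:7 to 5:7 neither test exceeds 4.8%.

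**The case for a change.** The best case for change is that the mechanism is exact and adjustment is cheap: some SAP wording and a different procedure call. With the assumed food effect and a 1.25-fold period effect, the planned shift is 2.39 to 2.41 h at 7:5 but 1.98 h at 5:7, while the adjusted shift is 2.20 to 2.22 h at both. The same truth is thus reported about 0.4 h apart according to which sequence lost subjects. At 6:6 the planned test gives up about 5 points of power at that period effect.

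Those results stand, but they depend on a period effect of about half an SD or more. The documents report none and suggest no cause: both periods use the same capsules and dose at one site, with standardised fasting and meals and continuous confinement (Protocol 2.0, 7.4.1, 8.1). At 1.1-fold the adjusted test still trails at 7:7, 6:6, 7:6, 6:7 and 7:5. The 46% chance of imbalance applies only after exactly two unreplaced losses, and the replacement numbering would tend to restore balance. Protocol 6.1 says that subjects with early emesis will be replaced; Protocol 6.3 and SAP 4.4 say that they may be.

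The contrast with Cmax and AUC is less of an inconsistency than it looks, because a paired signed-rank test takes no covariates. It is a deliberate and common choice for an untransformed time read off a sampling grid.

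**Conclusion.** No change follows; this is a fair trade-off. The pooled analysis does omit period, and at 7:5 its shift carries one sixth of any period effect. At 1.25-fold the bias across 7:6 and 7:5 is 0.07 to 0.17 h, or about 4 to 10 minutes, against 2 h gaps between samples around a 4 h peak and collection windows of ±10 to ±20 minutes there.

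Adjustment would not make the estimate more precise in the balanced settings checked. It narrows the interval and raises power at equal sequences only when the period effect is large. With no period effect it costs about 2 to 6 points of power and makes the interval 2 to 12% wider at splits from 7:7 to 5:7. If judged a major change to a primary-endpoint analysis, it would also need a protocol amendment under Protocol 11.1.

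The two-sample shift could be reported as an optional sensitivity analysis, but it would change no conclusion. Protocol 5.1 states no hypothesis, and no tmax criterion or sample size exists. The sizes rest on the assumed median, log-SDs and food effect, which were not varied; the period effect, the split and the time spread were.
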